11.5 Disease-Related Events and/or Disease-Related Outcomes Not Qualifying as SAEs

During the study period, the following conditions will not qualify as an AE or SAE provided they are not considered attributable to study medication:

- Cases of disease progression.

11.6 Pregnancy

Any pregnancy that occurs during study participation must be reported. To ensure subject safety, each pregnancy must be reported to the FDA with CC notification to INCYTE [contact] within 2 weeks of learning of its occurrence. The pregnancy must be followed up to determine outcome (including premature termination) and status of mother and child. Pregnancy complications and elective terminations for medical reasons must be reported as an AE or SAE. Spontaneous abortions must be reported as an SAE. Any SAE occurring in association with a pregnancy, brought to the investigator's attention after the subject has completed the study and considered by the investigator as possibly related to the investigational product, must be promptly reported to the pharmacovigilance group at the H. Lee Moffitt Cancer Center. In addition, the investigator must attempt to collect pregnancy information on any female partners of male study patients who become pregnant while the subject is enrolled in the study. Pregnancy information must be reported to the H. Lee Moffitt Cancer Center as described above.

11.7 Time Period and Frequency of Detecting AEs and SAEs

The investigator or site staff is responsible for detecting, documenting and reporting events that meet the definition of an AE or SAE. AEs will be collected from the start of Investigational Product and through the follow-up contact. SAEs will be collected

over the same time period as stated above for AEs. However, any SAEs assessed **as related** to study participation (e.g., investigational product, protocol mandated procedures, invasive tests, or change in existing therapy) will be recorded from the time a subject consents to participate in the study up to and including any follow-up contact. All SAEs will be reported to INCYTE [contact] within 24 hours, as indicated.

11.8 Prompt Reporting of Serious Adverse Events and Other Events to the FDA with notification to INCYTE

Any serious adverse events which occur during the clinical study or within 30 days of receiving the last dose of study medication, whether or not related to the study drug, must be reported by the investigator. In addition, any SAEs which occur as a result of protocol specific diagnostic procedures or interventions must also be reported. SAEs brought to the attention of the investigator at any time after cessation of ruxolitinib and considered by the investigator to be related or possibly related to ruxolitinib must be reported to FDA with notification to INCYTE [contact] if and when they occur. Additionally, in order to fulfill international reporting obligations, SAEs that are related to study participation (e.g., procedures, invasive tests, change from existing therapy) or are related to a concurrent medication will be collected and recorded from the time the subject consents to participate in the study until he/she is discharged.

Type of Event	Initial Reports		Follow-up Information on a Previous Report	
	Time Frame	Documents	Time Frame	Documents
All SAEs	24 hours*	“SAE” data collection tool	24 hours*	Updated “SAE” data collection tool
Pregnancy	2 Weeks*	Pregnancy Notification Form	2 Weeks*	Pregnancy Follow-up Form

- From the time point when the SAE or pregnancy became known to reporter.

11.9 Regulatory Reporting Requirements for SAEs

Prompt notification of SAEs by the investigator to the FDA (and INCYTE [contact]) is essential so that legal obligations and ethical responsibilities towards the safety of patients are met. The sponsor-investigator has a legal responsibility to notify both the local regulatory authority and other regulatory agencies about the safety of a product under clinical investigation. The sponsor-investigator will comply with specific regulatory requirements relating to safety reporting to the regulatory authority, /Institutional Review Board (IRB), the FDA, notification to INCYTE, and sub-investigators.² Investigator safety reports are prepared for suspected unexpected serious adverse reactions according to local regulatory requirements and those policies set forth by the FDA and are forwarded to investigators and INCYTE as necessary. An investigator who receives an investigator safety report describing an SAE(s) or other specific safety information (e.g., summary or listing of SAEs) from the H. Lee Moffitt Cancer Center will file it with the CIB and will notify the IEC /IRB, if appropriate according to local requirements.

12 PHARMACEUTICAL INFORMATION

12.1 Packaging and Labeling

Ruxolitinib 5 mg tablets are packaged as 60 counts in high-density polyethylene (HDPE) bottles. The bottles will include labeling “New Drug - Limited by Federal (USA) Law to Investigational Use.

12.2 Preparation

Tablets will be provided to the site and no specific preparation of study medication is required prior to administration.

12.3 Handling and Storage

Investigational product must be dispensed or administered according to procedures described herein. Only patients enrolled in the study may receive investigational product, in accordance with all applicable regulatory requirements. Only authorized site staff may supply or administer investigational product. All investigational products must be stored in a secure area with access limited to the investigator and authorized site staff and under physical conditions that are consistent with investigational product-specific requirements. The bottles of tablets should be stored

at room temperature, 15°C to 30°C (59°F to 86°F). Any unused investigational product will be returned to INCYTE for destruction or destroyed at the institution per institutional policy (if allowable).

13 Study Calendar

All screening evaluations will be performed within 4 weeks prior to the start of ruxolitinib treatment. Patients must have a bone marrow biopsy and aspirate (including cytogenetics) performed within 4 weeks prior to the start of treatment. All transfusion and pre-transfusion Hgb or platelet count must be recorded for the 8 weeks prior to initiation of study treatment. Strict adherence to the visit schedule is required. In the event that a visit or test cannot be scheduled on the exact visit day, a window of ± 7 days is allowable. Bone marrow aspiration and biopsy exams can be done within a 14 day window of the allotted date.

13.1 Baseline Assessment: within 4 weeks of starting treatment

- Medical history including:
 - Disease characteristics such as date of diagnosis of CMML, WHO/FAB subtype, IPSS score, MD Anderson Scoring System (MDASC), prior treatments.
 - ECOG performance status.
- Concurrent medication review.
- Red blood cell and platelets transfusion past 8 weeks.
- Routine physical examination to include vital signs, height and weight.
- Bone marrow examination, including cytomorphology, cytogenetic assessment, and flow cytometry analysis. Possibly include NGS myeloid panel (it is not considered a deviation if cytogenetic, flow cytometry and NGS myeloid panel is not completed).
- Laboratory assessments:
 - Hematology to include platelet count, hemoglobin, hematocrit, white blood cells (WBC) and WBC differential (including: neutrophils, eosinophils,

basophils, lymphocytes and monocytes), INR, PT, and PTT and reticulocyte count.

- Clinical chemistries including BUN/urea, creatinine, chloride, sodium, potassium, alkaline phosphatase, alanine aminotransferase (ALT), aspartate aminotransferase (AST), total bilirubin, bicarbonate, calcium, chloride, glucose, LDH, total protein, and albumin.
- Urine or serum pregnancy test for females of childbearing potential will be performed at Screening or on Day 1, prior to first dose study medication.
- Symptom Score using the Myeloproliferative Neoplasms Symptom Assessment Form (MPN-SAF). (See Appendix C).
- CT scan of the abdomen to evaluate spleen volume.
- Review and record any blood and blood supportive care products for the prior 8 weeks.

Re-screening

Bone marrow biopsy and CT scan of the abdomen may not need to be repeated for a re-screening process if they are completed within 3 months from the time of consenting on the study. Although, all the other procedures including labs, Myeloproliferative Neoplasms Symptom Assessments, research labs (research lab exclude aspirate) will be performed during the re-screening process within 4 weeks prior to the start of the study treatment.

Patient can be re-screened and start the first day of treatment on the same day if patient meets the eligibility criteria on the study.

13.2 Treatment Period (weeks 1-16):

- 13.2.1 Ruxolitinib will be administered as a twice daily oral dose for a 4-week treatment cycle. Patients will have a CBC with leukocyte differential performed weekly for the first 16 weeks. Serum chemistry will be performed weekly for first 4 weeks and then every 2 weeks through week 16. A BM aspirate and biopsy with cytogenetic analysis will be performed after cycle 2 and 4 (at the end of week 8 and week 16) to assess pathologic response, cytogenetic response and disease progression. For patients who achieve CR, marrow CR, or PR a confirmation bone marrow aspirate and biopsy should be obtained 4 to 8 weeks after documentation of CR, marrow CR, or PR.

13.3 **End of C4/ Week 16 Response Assessment:** Patients will complete a response assessment (see Section 14) within one week after their last administration of ruxolitinib. . Physical exam, vital signs, concomitant medication, adverse event reporting, CBC, CT scan of the abdomen, serum chemistry and BM aspirate and biopsy with cytogenetic analysis will be performed.

13.4 **Continuation Phase:** After completing cycle 4 response assessments, responders may continue to receive ruxolitinib and the final week 16 dose in the absence of DLT or disease progression. Bone marrow biopsy and aspirate will be

repeated after every 6 cycles (For patients who achieve CR, marrow CR, or PR a confirmation a one-time bone marrow aspirate and biopsy should be obtained 4 to 8 weeks after documentation of CR, marrow CR, or PR). A CBC will be obtained and complete metabolic profile as per standard of care. The End of Treatment assessment should be done within a week off treatment.

13.5 **End Of Treatment:** Patients discontinuing study early or any time after completing End of C4/Week 16 Response Assessment visit should complete their end of treatment visit within two weeks after their last dose of investigational product. Physical exam, vital signs, concomitant medication, adverse event reporting, CBC, CT scan of the abdomen, blood chemistry and BM aspirate and biopsy with cytogenetic analysis will be performed during the end of treatment visit. CT scan abdomen and BM aspirate and biopsy during EOT can be performed at the discretion of Coordinating Center PI.

13.6 **Off Treatment assessment:** includes best response achieved, date of first response, date of loss of response, reason for discontinuation.

13.7 **Off study evaluation:** include vital status, date of death/last contact, transformation to AML and the date of transformation to AML if applicable. This Evaluation will be updated every 6 month for 2 years.

Study Calendar	Pre-Study	C1/Wk 1	Wk 2	Wk 3	Wk 4	C2/Wk 5	Wk 6	Wk 7	Wk 8	C3/Wk 9	Wk 10	Wk 11	Wk 12	C4/Wk 13	Wk 14	Wk 15	Wk 16	End of C4 Response Assessment	Biweekly (every 2 weeks, after End of C4 response assessment)	Continuation Phase-4 Every 4 weeks (if response)	Off-Study or EOT-
Ruxolitinib Dispense ^a		X				X				X				X				X		Xa1	
Informed consent	X																				
Demographics	X																				
Medical history	X					X				X				X				X		X	X
Physical exam to include spleen assessment	X					X				X				X				X		X	X
Vital signs	X					X				X				X				X		X	X
Height ¹	X																				
Weight	X					X				X				X				X		X	X
Performance Status	X					X				X				X				X		X	X
Concurrent medication review	X																				
CBC w/diff, plts,	X	X	X	X	X	X	X	X	X	X	X	X	X	X	X	X	X	X	X	X	X
Retic Count	X					X				X				X				X			
Serum chemistry ^b	X	X	X	X	X		X		X		X		X		X		X	X	X ^{b1}	X	X
INR, PT, and PTT	X																				
Adverse event evaluation		X ----- X Adverse events will be summarized and reported prior to each cycle.																			
Bone marrow	X									X								X			

biopsy/aspirate ^d ***																				
B-HCG ^c	X																			
Lab. Correlates ^e	X					X				X									X	
Prior CMML Treatments	X																			
CT scan Abdomen ^h	X																		X	X
Transfusion Log	X					X				X									X	X
Response Assessments										X									X	X
Symptom Score Scale ^f	X	X	X	X	X	X	X	X	X	X	X	X	X	X	X	X	X			
Off-treatment Assessment/Off-Study Follow-up/ CMML Summary Form																			X	X

- a. Dose as assigned for cohort in phase 1, dose assigned as MTD in phase 2. Ruxolitinib dispensing will take place on day 1 of each 4 week cycle. Any lost study drug may be re-dispensed as needed.
- b. Albumin, alkaline phosphatase, bicarbonate, BUN, calcium, chloride, creatinine, glucose, LDH, potassium, total protein, AST, ALT, sodium, and total bilirubin.
- b1. Biweekly Serum chemistry is optional after the completion of End of C4 Response Assessment; however, it is mandatory to complete serum chemistry every cycle (monthly serum chemistry is required on the study protocol).
- c. Serum or urine pregnancy test (if women of childbearing potential).
- d. In addition to specimen required for pathologic review, and additional aspirate will be collected (goal volume of 30cc). BM biopsy will occur at screening, end of Week 8, and Week 16. Week 8 and Week 16 BM biopsies have a window of +/- 14 days. In the event patient has CR or PR see Section 13.2.1 for additional one time BM biopsy.
- e. In addition to specimen required for routine labs, 6 green top vials, 1 red top vial.
- f. The Myeloproliferative Neoplasms Symptom Assessment Form (MPN-SAF TSS) using ERT's DiaryPro done by the patient. Data upload and device maintenance will occur at each scheduled visit through Week 16. Patient cannot be enrolled on the study protocol without ERT's DiaryPro registration. No waiver on the ERT handheld device will be given in any circumstances.
- g. BM aspirate and biopsy includes mutational panel should be performed every 6 cycles (window of +/- 14days) after completion of week 16 on the treatment.

h. CT scan abdomen may be completed with/without contrast.

i. Height is preferred to be recorded as a baseline; however, missing height during the screening process will not be a deviation on the study protocol.

*End of C4/ Week 16 Response Assessment and End of Treatment: Patients will complete a response assessment within one week after their last administration of ruxolitinib. Patients discontinuing study early should complete their end of treatment visit within two weeks after their last dose of investigational product. Physical exam, vital signs, concomitant medication, adverse event reporting, CBC, and serum chemistry and BM aspirate and biopsy with cytogenetic analysis will be performed.

**Continuation Phase: After completing cycle 4 response assessments, HI-platelet responders may continue to receive ruxolitinib and the final week 16 dose in the absence of DLT or disease progression. Bone marrow biopsy and aspirate will be repeated after every 6 cycles. A CBC will be obtained and complete metabolic profile as per standard of care. The off treatment assessment should be done within a week off treatment.

For patients who achieve CR, marrow CR, or PR a confirmation bone marrow aspirate and biopsy should be obtained 4 to 8 weeks after documentation of CR, marrow CR, or PR.

***Off Treatment assessment: includes best response, date of first response, date of loss of response, reason for discontinuation.

****Off study follow up: include vital status, date of death/last contact, transformation to AML and the date of transformation to AML if applicable. This evaluation will be updated every 6 months for 2 years.

*****Myeloproliferative Neoplasms Symptom Assessment Form: The Myeloproliferative Neoplasms Symptom Assessment Form (MPN-SAF TSS) can be completed on paper in case an electronic assessment on ERT is not available on the day of screening and rescreening visits. In the event there is a discrepancy of MPN assessment score on paper and electronic assessment, the treating physician will determine which assessment will be used for eligibility purposes on the study.

*****All dates are entered into the database (Oncore) in +/- one week from the date of visit complete

***** During the pandemic or any contrary circumstances, monthly visits may be a zoom/virtual visit per Investigator discretion only after the completion of week 16 on the study protocol. However, patients have to complete all the safety labs and study-related procedures/tests on the study protocol. Any missed procedures will be a deviation excluding vital signs and physical exam.

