Treatment plan	
Treatment will be administered on an outpatient basis. Reported adverse events and potential risks are described in Section 11. Appropriate dose modifications for ruxolitinib are described in Section 10. No investigational or commercial agents or therapies other than those described below may be administered with the intent to treat the patient's CMML. Ruxolitinib will be supplied by INCYTE as 5mg tablets. .
 
Ruxolitinib will be self-administered as a twice-daily oral dose for a continuous treatment cycle. Ruxolitinib tablets will be taken approximately 12 hours apart (morning and night). Patients will not take the morning dose of ruxolitinib at the first regularly scheduled visit.. On all other days corresponding to study visits, patients will take the morning dose of study drug prior to the visit, and will note on the subject reminder card the time that medications were taken.
 
Patients will also be instructed to take ruxolitinib without respect to food, as previous data demonstrate no change in drug kinetics or absorption. All patients will be given 40 mg/day divided in equal BID doses. A maximum of 29 patients will be treated at the MTD identified in phase I of 20mg BID. See study calendar for assessment on study.

Dose delay/modifications	
Dose delays/modifications are allowed for those patients enrolled in phase II as described in section 6.

Duration of Therapy	
Patients will be treated for a total of 16 weeks. For patients responding at week 16, treatment may continue until one of the following criteria applies:
 
 • Intercurrent illness that prevents further administration of treatment. • Unacceptable adverse event(s). • Patient decides to withdraw from the study. • General or specific changes in the patient's condition render the patient unacceptable for further treatment in the judgment of the investigator. • Evidence of disease progression by the IWG MDS/MPN criteria.

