Duration of Follow-Up	
Patients will be followed as per calendar on treatment for 17 weeks. After 17 weeks, patients who continue on study will be followed monthly. Off study data on AML transformation and overall survival will be updated every 6 months or until death, whichever occurs first. Patients removed from the study for unacceptable adverse events will be followed until resolution or stabilization of the adverse event.
 
Criteria for Removal from Study Study drug treatment can continue for patients receiving clinical benefit per IWG criteria, unless: one or more withdrawal criteria are met, or at the subject's discretion, or if the study is terminated. *Subject Completion

	
A subject will be considered to have completed the study if the subject meets at least 1 of the following criteria:
 
 - The subject has completed 16 weeks of treatment with study medication with no improvement. - The subject died during the study. - The subject experienced an adverse event (AE) that lead to withdrawal from the study. 
*Subject Withdrawal from Study A subject may voluntarily withdraw from study medication or withdraw consent from the study at any time. The investigator may also, at his or her discretion, discontinue a subject from participating in the study at any time. The investigator will record the date and the reason for subject withdrawal from the study.
 
*Subject Withdrawal from Study Medication If the subject is permanently withdrawn from treatment with study medication, but does not withdraw consent, the investigator must make every effort to have the subject complete all withdrawal assessments at the time of withdrawal, and complete all scheduled follow-up visits.
 
Treatment: with study medication must be discontinued if (Withdrawal Criteria):
 
 • No clinical benefit has been attained after 16 weeks of treatment. • Evidence of Disease progression according to IWG MDS/MPN criteria. • A subject becomes pregnant. • A subject is significantly non-compliant with the requirements of the protocol. • A subject has an adverse experience that would, in the investigator's judgment, make continued participation in the study an unacceptable risk.
Follow up on study	See calendar page 36

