9.3 Subject Withdrawal from Study Medication

If the subject is permanently withdrawn from treatment with study medication, but does not withdraw consent, the investigator must make every effort to have the

subject complete all withdrawal assessments at the time of withdrawal, and complete all scheduled follow-up visits. Treatment with study medication must be discontinued if:

- The subject withdraws consent.
- Further participation would be injurious to the subject's health or well-being in the Investigator's medical judgment.
- The study is terminated.
- The subject becomes pregnant
- The patients exhibits leukemic transformation (as evidenced by bone marrow blast counts of at least 20%, or peripheral blast counts of at least 20% lasting at least 8 weeks.
- No clinical benefit has been attained after 16 weeks of treatment.
- Evidence of Disease progression according to IWG MDS/MPN criteria.
- a subject is significantly non-compliant with the requirements of the protocol.
- a subject has an adverse experience that would, in the investigator's judgment, make continued participation in the study an unacceptable risk.

Patients withdrawing from study can be tapered off of ruxolitinib over a 4 week period at the discretion of the investigator

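### Study Calendar footnote ** names only platelet responders for continuation after cycle 4, while the rest of the protocol sets no lineage limit

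*Combined protocol and SAP*

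**What the plan says.** Several places in the combined protocol and SAP say who may stay on ruxolitinib after the week-16 assessment.

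- Section 13, Study Calendar, footnote ** (Continuation Phase): "After completing cycle 4 response assessments, HI-platelet responders may continue to receive ruxolitinib".
- Section 13.4 (Continuation Phase): "After completing cycle 4 response assessments, responders may continue to receive ruxolitinib".
- Synopsis (Duration of Therapy) and Section 7, in one shared sentence: "For patients responding at week 16, treatment may continue until one of the following criteria applies".
- Synopsis (Criteria for Removal from Study): "Study drug treatment can continue for patients receiving clinical benefit per IWG criteria".
- Study Calendar, continuation column header: "Every 4 weeks (if response".
- Section 9.3, the one mandatory stop that rests on lack of response: "No clinical benefit has been attained after 16 weeks of treatment". The other listed reasons are consent withdrawal, harm, study termination, pregnancy, leukemic transformation, progression, non-compliance and an adverse experience.

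Two provisions bear on follow-up after stopping. Section 9.3 asks for every effort to have the patient "complete all withdrawal assessments at the time of withdrawal, and complete all scheduled follow-up visits". The off-treatment record in Section 13.6 "includes best response achieved, date of first response, date of loss of response, reason for discontinuation".

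**The concern.** The footnote names a narrower group than any other passage on continuation. Sites commonly run visits from the calendar, and Section 13 asks for strict adherence to its schedule. A site that took the footnote at face value could stop drug in a patient whose week-16 response was in the spleen, symptoms, red cells or neutrophils, although every other passage would let that patient continue.

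Duration of response (3.2.3) is what is at stake. It needs responders to be observed until the response is lost. Once a patient is off study, the evaluation in Section 13.7 lists vital status and AML transformation, not response. If stopping depended on which footnote or section a site followed, the length of on-treatment follow-up would vary for reasons unrelated to the disease.

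**Working it through.** No figure in the plan depends on this wording, so the check is a comparison of text. I take HI-platelet to mean the platelet response in Section 14.

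**Step 1. The passages side by side.**

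| Place | Group named | Limited to one lineage? |
|---|---|---|
| Calendar footnote ** | HI-platelet responders | Yes |
| Section 13.4 | responders | No |
| Synopsis (Duration of Therapy); Section 7 | patients responding at week 16 | No |
| Calendar column header | patients with a response | No |
| Synopsis (Criteria for Removal) | patients with clinical benefit | No |
| Section 9.3 (stop rule) | stops those without clinical benefit | No |

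Footnote ** and Section 13.4 largely share their wording, including the opening clause, the continued week-16 dose and the marrow examination every 6 cycles. The main difference in who may continue is the added platelet term.

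**Step 2. How much narrower the footnote is.** The Section 14 Clinical Benefit list has five items: erythroid, platelet, neutrophil, spleen and symptom. The footnote names 1 of 5 and leaves 5 − 1 = 4 unnamed. This counts categories, not patients. Inclusion criterion 4.1.9 requires symptomatic splenomegaly and/or a symptom score above 17, so two of the unnamed categories, spleen and symptom, correspond to the features on which patients are selected.

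**Step 3. Whether the other passages agree among themselves.** None sets a lineage limit, but they use two terms. The shared synopsis and Section 7 sentence, Section 13.4 and the column header speak of response. The synopsis removal criteria and Section 9.3 speak of clinical benefit. The terms are not interchangeable: endpoint 3.1.1 counts stable disease as clinical benefit, and the Section 14 list does not. A patient with stable disease at week 16 has clinical benefit under 3.1.1, but it is not stated whether that patient is a responder.

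**Step 4. What depends on continuation.** The primary endpoint is read at week 16, and the footnote applies only after the cycle 4 assessment. The Simon design in Section 15.2 uses only 1/10, 5/29, 10% and 30%. Exact binomial sums give:

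- early termination under the null: 0.736 (stated 0.74)
- type I error: 0.047 (stated 0.05)
- type II error: 1 − 0.8051 = 0.1949 (stated 0.19)

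None of these inputs involves treatment after week 16. Of the endpoints, duration of response is the one exposed.

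**Step 5. Number of patients.** This would require the split of week-16 responses by type. The documents give none, so no count is offered.

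**The case against.** The strongest reply is that this is a stray word. The footnote says that platelet responders may continue and orders nobody to stop. It otherwise follows Section 13.4. The note directly beneath it schedules a confirmatory marrow for patients with CR, marrow CR or PR, so the calendar notes do not overlook those patients. The mandatory stops are in Section 9.3, and a non-platelet response is not among them. Sections 9.3 and 13.6 also provide for follow-up visits and for recording the date of loss of response.

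All of this stands, and it keeps the point small. It does not remove the contradiction: the footnote is operative text, and nothing says that the sections override it.

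A reader might infer four stronger things that the documents do not support.

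- *That non-platelet responders must stop.* The footnote is permissive.
- *That one passage is outvoted by five.* The synopsis and Section 7 repeat one sentence, and the passages divide between two terms, so a tally overstates their agreement.
- *That loss of a symptom response after week 16 could not be dated, because footnote f ends diary upload at week 16.* Footnote f limits upload and device maintenance, not diary entry. Section 14 keeps nightly entry going until treatment is discontinued, provides for download at study visits as applicable, and archives the data when the device is returned at the end-of-treatment visit. The calendar's symptom row is damaged in the extracted text and adds little.
- *That objective 1.2.3 would cause AML transformation to be timed in place of response.* The objective plainly concerns duration of response. Its pointer to the first secondary endpoint is a slip, and Section 15 never uses it.

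**Conclusion.** The contradiction is real and minor. Footnote ** names a narrower continuation group than the synopsis, Section 7, Section 9.3, Section 13.4 and the calendar's own column header. If a site followed it, on-treatment follow-up of non-platelet responders could be shortened, with a possible effect on duration of response. The primary endpoint, the sample size and the error rates do not change.

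The wording mismatch is certain. The consequence is conditional: it assumes that some site works from the footnote rather than the sections, and its size cannot be estimated. Section 15 also describes no analysis of duration of response, so the effect on a reported result cannot be traced further. Which continuation rule is right is a clinical matter and is not judged here.

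**What to change.** Reconcile footnote ** with the synopsis (Duration of Therapy and Criteria for Removal), Section 7, Section 9.3, Section 13.4 and the calendar column header, so that one continuation rule is stated throughout. Use one term, either response or clinical benefit, and say whether it includes stable disease, since 3.1.1 and the Section 14 list differ. The clinical team decides which rule applies.

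Two editorial corrections can go in at the same time:

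- Align the upload wording in footnote f with the symptom assessment text in Section 14.
- In objective 1.2.3, stated in both the synopsis and Section 1, replace the pointer to AML transformation (3.2.1) with the name of the response being timed.

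The cost is wording only: two footnotes, one objective in two places, and consistent use of one term in the listed sections. These edits change no visit, sample size or analysis of the primary endpoint.
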